#### **4.3. Discontinuation Criteria**

##### **4.3.1. Screen Failures**

Screen failures are defined as patients who consent to participate in the clinical trial but do not meet all eligibility criteria and are not dosed in the trial. A minimal set of information is required to ensure transparent reporting of screen failure patients to meet the Consolidated Standards of Reporting Trials (CONSORT) publishing requirements and to respond to queries from regulatory authorities. Minimal information includes demographics, reason for screen failure, eligibility criteria, and any SAEs.

Final assessment of the eligibility criteria is done prior to first dose. Patients who do not meet the criteria for participation in this trial may be rescreened.

##### **4.3.2. End of Treatment**

The end of treatment (EOT) is defined as the day the last dose of Lu-DTPA-omburtamab is received. The EOT Visit should occur 5 to 6 weeks after the last dose, whether this is a premature treatment discontinuation or treatment completion.

###### ***4.3.2.1. Discontinuation of Trial Treatment***

Patients may withdraw from the trial treatment at any time at his/her own request or may be discontinued from trial treatment at any time at the discretion of the investigator for safety, behavioral, or administrative reasons. If the patient withdraws consent for disclosure of future information, the sponsor may retain and continue to use any data collected before such a withdrawal of consent. Additionally, patients may request destruction of any samples taken and not tested, and the investigator must document this in the site trial records. Refer to the Schedule of Assessments ([Appendix 3](#)) for data to be collected at the time of treatment discontinuation (EOT visit) and follow-up and for any further evaluations that need to be completed.

The patient must be permanently discontinued from treatment if any of the following occur:

- After receiving the dosimetry dose only, Grade 3 or 4 non-hematologic AE (including an AE considered to be a Grade 3 or 4 nervous system disorder; see [Section 7.1.5](#))
- DLT occurring before the end of Cycle 1 in each dose level in Part 1
- Grade 4 infusion-related reaction/anaphylaxis, or Grade 3 infusion-related reactions (excluding fever and Grade 3 abnormal laboratory values) that do not resolve to Grade  $\leq$  1 within 5 days of onset

- Grade 4 neurological AE
- Development of obstructive or symptomatic communicating hydrocephalus
- Grade 4 treatment-related AEs (excluding infusion-related fever, and non-life-threatening laboratory values)
- Disease progression before Cycle 2 in Part 1 or Cycle 5 in Part 2
- Any medical or safety reason, in the opinion of the investigator or sponsor
- Chemical meningitis (symptoms of clinical meningitis but cultures for infectious agents were negative) in which either: a) event is non-responsive to IV steroids, b) radiologic or operative intervention was indicated, or c) focal neurologic deficit was present
- The patient receives prohibited therapy and/or undergoes procedures during the trial that, in the opinion of the investigator, warrant treatment discontinuation
- Patient decision
- Pregnancy.

A patient who is discontinued from treatment, but for whom consent is not withdrawn, shall continue to be followed for the entire trial period.

#### **4.3.2.2. *Completion of Trial Treatment***

Patients will be regarded as having completed the trial treatment if they received 2 cycles of IMP in Part 1 or up to 5 cycles in Part 2.

#### **4.3.3. *End of Trial***

The end of the trial is defined as the date the last patient completes the last Visit or the date of death of the last patient, whichever comes first.

##### **4.3.3.1. *Discontinuation from Trial***

A patient should be discontinued from the trial if:

- The patient or legal guardian withdraws informed consent for any reason.

##### **4.3.3.2. *Completion of Trial***

Patients will be regarded as having completed the trial if they received all the planned cycles and attend the EOT visit (Part 1) and follow-up period (Part 2) until the end of trial.

#### **4.3.3.3. *Lost to Follow-up***

A patient will be considered lost to follow-up if he/she repeatedly fails to return for scheduled visits and is unable to be contacted by the trial site.

If a patient fails to return to the clinic for a required trial visit, the site must attempt to contact the patient and reschedule the missed visit as soon as possible, counsel the patient on the importance of maintaining the assigned visit schedule, and ascertain whether or not the patient wishes to and/or should continue in the trial.

In cases in which the patient is deemed lost to follow-up, the investigator or designee must make every effort to regain contact with the patient (where possible, 3 telephone calls and, if necessary, a certified letter to the patient's last known mailing address or local equivalent methods). These contact attempts should be documented in the patient's medical record.

Should the patient continue to be unreachable, he/she will be considered to have discontinued from the trial with a primary reason of lost to follow-up.

#### **4.3.4. *Replacement Procedures***

Patients in Part 1, who discontinue treatment after the Dosimetry dose (i.e., prior to the first treatment dose), will be replaced. Patients in Part 1, who are discontinued during the DLT reporting period for reasons not related to IMP may be replaced following discussion between the investigator and the sponsor. If a patient is discontinued as a result of AEs considered to be related to the IMP, the DMC will be consulted as to whether the patient should be replaced.

#### **4.3.5. *Follow-up of Patients Discontinued from Trial Treatment or from the Trial***

A patient discontinued from treatment should as soon as possible attend the EOT Visit, and be followed at all scheduled Follow-up Visits (Part 2) and for post-trial monitoring of secondary malignancies at least 10 years after end of trial, or until death, if sooner ([Appendix 3](#)).

The investigator should:

- Ensure the safety of the patient. Follow any SAE and Grade 3 or higher non-serious AEs that are considered treatment related and still ongoing after withdrawal until the event has been resolved or the investigator assesses the SAE as being chronic or stable.
- Offer the best possible treatment outside of the trial based on clinical practice at the investigational site.

#### **4.4. *Data Monitoring Committee***

An external DMC will be established to assure patient safety and will function independently of all other individuals associated with the conduct of the trial, including site investigators participating in the trial. The DMC will consist of a minimum of 2 physicians whose expertise covers relevant specialties.

During the conduct of Part 1, following completion of the first 5-week treatment cycle (Cycle 1) for the last patient in each dose level, the DMC will evaluate available safety information and recommend trial continuation or termination. If continuation is recommended, the DMC will recommend to the sponsor whether the dose should be escalated, de-escalated, or held at the same level. In the absence of DLT during the first two weeks of the first patient enrolled in each dose level, the enrollment to the dose level will continue without the need of feedback from the DMC.

If any of the side effects mentioned in the DLT definitions ([Section 3.1.1.2](#)) occurs during Cycle 2 in Part 1, these will be discussed at the first upcoming preplanned DMC meeting, and the internal Sponsor Safety Committee will evaluate the external DMC recommendations for further dosing. During Part 1 and until the DMC meeting in Part 2, the sponsor will share with the DMC all SAEs occurring during the trial and an unplanned DMC meeting can be held at the request of either the DMC or the Sponsor Safety Committee.

The DMC will evaluate the totality of cumulated absorbed dose calculated based on the dosimetry data from Part 1, and all available DLTs and other non-DLT toxicities from cycles 1 and 2 in all patients dosed in Part 1, to guide whether the maximum of five cycles is feasible in Part 2.

During the conduct of Part 2, an additional DMC meeting will be held when the eighth patient has completed dosing in Cycle 1 to evaluate whether the trial should be modified, stopped, or continue unchanged. The Sponsor Safety Committee will evaluate the recommendations from the DMC after each DMC meeting. Any significant finding/recommendation from the DMC and endorsed by the Sponsor Safety Committee will be communicated to the regulatory authorities and Institutional Review Board (IRB)/Ethics Committee (EC) as appropriate, and to the sites.

Responsibilities, procedures, content of the DMC packages, and workflow of the DMC are specified in the DMC Charter.

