**Methodology/trial design:**

This is a Phase I/II, open-label, safety and efficacy trial in pediatric and adolescent patients (3 to 19 years) with recurrent or refractory medulloblastoma.

Part 1 will be a dose-escalation phase with a 3+3 sequential-group design (except for the first dose level, which will consist of a single patient only), in which patients will receive a maximum of two 5-week cycles of treatment with intracerebroventricular Lu-DTPA-omburtamab. A Data Monitoring Committee will review the safety data from previous dose levels and provide recommendations on whether dose escalation should continue. In Part 1, Cycle 1 will comprise a dosimetry dose on Day 1 and a treatment dose on Day 8, while Cycle 2 will comprise a treatment dose on Day 1. Successive dosing groups will receive escalating treatment doses of lutetium-177 conjugated to a fixed mass dose of approximately 1 mg DTPA-omburtamab; the dosimetry dose will be fixed for all patients.

Part 2 will be a cohort-expansion phase in which patients will receive a maximum of 5 cycles of intracerebroventricular Lu-DTPA-omburtamab at the RP2D determined in Part 1. All cycles in Part 2 will comprise a treatment dose on Day 1.

The AEs will be evaluated according to CTCAE version 5.0.

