In Part 2, all treatment cycles will consist of a treatment dose on Day 1; the dose level will be the RP2D determined in Part 1. Patients who are not discontinued from treatment will be eligible for up to 5 treatment cycles in Part 2. Dose reductions due to toxicity are permitted in Part 2 only.

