## 2. OBJECTIVES AND ENDPOINTS

### 2.1. Objectives

#### 2.1.1. Primary Objectives

The primary objective of Part 1 (dose-escalation phase) of this trial is to explore the tolerability of up to 2 cycles of intracerebroventricular Lu-DTPA-omburtamab treatment in pediatric and adolescent patients with recurrent or refractory medulloblastoma. The MTD and/or the RP2D for Part 2 will be determined.

The primary objective of Part 2 (cohort-expansion phase) of this trial is to establish a safety profile of repeated dosing of Lu-DTPA-omburtamab in pediatric and adolescent patients with recurrent or refractory medulloblastoma.

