### 3.1.1. Part 1 (Dose-escalation Phase)

Part 1 will comprise 1 dose level consisting of a single patient followed by additional dose levels that use a 3+3 design (see [Figure 1](#)).

In the first 5-week treatment cycle, a 5 mCi dosimetry dose will be administered on Day 1 and a treatment dose (according to the assigned dose level, as listed below) will be administered on Day 8 (see [Figure 1](#) for a schematic of a treatment cycle in Part 1). However, if a patient experiences a Grade 3 or 4 non-hematologic AE (including an AE considered to be a Grade 3 or 4 nervous system disorder) or other DLT after receiving the dosimetry infusion, the treatment dose will not be administered, and the patient will be discontinued from trial treatment. If the dosimetry dose of 5 mCi turns out to deliver a too low acquisition of radioactivity count (see [Section 7.2](#)), the dosimetry dose will be increased to 10 mCi for subsequent patients, at the sponsor's discretion.

A fixed mass dose of approximately 1 mg DTPA-omburtamab will be labelled with increasing radioactivity doses. This mass dose was selected based on the clinical experience with iodine-labelled omburtamab, in which the same mass dose has been shown to be stable and to support clinical use in concentrations up to 100 mCi/ml. The planned radioactivity dose levels are:

- Dose Level 1 (1+2 patients): 10 mCi
- Dose Level 2 (3+3 design): 25 mCi
- Dose Level 3 (3+3 design): 50 mCi
- Dose Level 4 (3+3 design): 65 mCi
- Dose Level 5 (3+3 design): 85 mCi.

A maximum of 1 additional intermediate dose level may be added to the trial if warranted based on the findings from previous dose levels (see [Section 3.1.1.1](#)).

[figure not shown]
Patients who are not discontinued from treatment (according to the criteria in [Section 4.3.2](#)) will be eligible for a second treatment cycle at the same dose administered in the first cycle. The second treatment cycle will not include a dosimetry dose but will instead consist of a treatment dose on Day 1 of the cycle.

In Part 1, the patients will receive a maximum of 2 treatment cycles. Patients who do not experience a DLT will be eligible for Cycle 2 dosing at the same dose administered in Cycle 1. Cycle 2 dosing will not include a dosimetry dose but only a treatment dose on the first day of the cycle.

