### ***3.1.1.1. Dose Escalation and Stopping Rules***

As detailed in [Section 4.4](#), a DMC will be formed to independently review the safety data from previous dose level(s) and make recommendations on whether dose escalation should continue. Based on the DMC recommendation, following review by the sponsor, the doses may be escalated or reduced and may be lower than the starting dose.

The starting treatment dose of lutetium-177 in Part 1 will be 10 mCi. Planned dose escalations (with a 3+3 design) are 25, 50, 65, and 85 mCi. Up to 1 additional dose level may be recruited to investigate an intermediate dose of investigational medicinal product (IMP), if warranted based on the safety findings from previous dose level(s). The requirement for an additional dose level will be agreed with the sponsor in consultation with the DMC and will be documented in the

Trial Master File. Dosing at any additional dose level will be subject to the same dose-escalation rules as for the planned dose levels, as described below. The maximum planned dose is 85 mCi.

Initially, 1 patient will be allocated to Dose Level 1 and subsequent dose escalations will be conducted using a classic 3+3 design. If no treatment-related Grade 3 or higher AEs are observed in the first patient, escalation from Dose Level 1 to Dose Level 2 will proceed with 3 patients being allocated to Dose Level 2, after DMC evaluation and recommendation. If a Grade 3 or higher treatment-related AE occurs, a further 2 patients will be enrolled at Dose Level 1.

The DMC will receive all SAE on an ongoing basis. The DMC will make the final assessment of whether the event qualifies as a DLT.

The first enrolled patient in each dose level will be observed for a minimum of two weeks after the treatment dose before subsequent patients will be dosed at the same dose. During the two weeks of observation, safety surveillance will focus on DLTs (including myelosuppression). If a DLT is observed in the first patient, a second patient will be included and observed for a minimum of two weeks after the treatment dose before the third patient is included. If no DLT is observed in the first patient, two subsequent patients will receive the treatment dose, but at least two days apart.

Escalation and de-escalation decisions will then be determined by the number of DLTs (as defined in [Section 3.1.1.2](#)) observed during Cycle 1 and the number of patients evaluable for DLTs, as follows.

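### No planned DMC review in Part 2 is assured to include observed Cycle 3 to 5 data, and the commitment to share SAEs ends at the one meeting that is planned

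*Combined protocol and SAP*

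**What the plan says.** Section 4.4 gives the DMC these tasks that bear on Part 2.

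- **One planned meeting.** In Part 2, "an additional DMC meeting will be held when the eighth patient has completed dosing in Cycle 1", to advise whether the trial is modified, stopped or left unchanged. The Synopsis states: "All cycles in Part 2 will comprise a treatment dose on Day 1". Cycle 1 dosing is therefore complete on the eighth patient's Day 1.
- **Data flow.** "During Part 1 and until the DMC meeting in Part 2, the sponsor will share with the DMC all SAEs occurring during the trial". The same sentence then lets the DMC or the Sponsor Safety Committee ask for an unplanned meeting. Read naturally, its opening time limit covers that provision too.
- **Feasibility of five cycles.** The DMC evaluates Part 1 dosimetry, and the toxicity of Cycles 1 and 2 in Part 1, "to guide whether the maximum of five cycles is feasible in Part 2".

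On exposure, Section 3.1.1 states: "In Part 1, the patients will receive a maximum of 2 treatment cycles". For Part 2 the Synopsis states: "Patients who are not discontinued from treatment will be eligible for up to 5 treatment cycles in Part 2". The Part 2 primary objective in Section 2.1.1 is "to establish a safety profile of repeated dosing".

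Section 3.2 describes DMC safety monitoring for Part 1 only. Two provisions carry no end date: the stopping rules in Section 4.4.1, and the notification of significant safety issues in Section 7.4.5.6. Section 4.4 leaves package content and workflow to the DMC Charter, which is not among the documents.

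**The concern.** Cycles 3, 4 and 5 are given for the first time in Part 2, and their safety is what Part 2 is primarily meant to describe. The only scheduled independent look is keyed to a first dose, not to accumulated dosing. How much later-cycle experience it contains depends on accrual speed, which the protocol does not control or state for Part 2. After that meeting the explicit commitment to send SAEs to the DMC lapses.

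In Part 1 the DMC meets after the last patient at a level has completed the five-week Cycle 1. In Part 2 the trigger requires no follow-up of the eighth patient.

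At stake is whether an independent committee sees the cumulative-dose experience while it can still affect patients, in a first-in-human paediatric radioimmunotherapy trial. The analysis section does not fill the gap. Section 8.3 places the full Part 2 safety analysis at the last patient's week 52 (or death or loss to follow-up), after dosing has ended on the nominal schedule. Section 8.9 provides only ad hoc interim analyses linked to communication with regulators.

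**Working it through.** **The plan's own figure.** Section 8.1 says 24 patients give at least 90% probability of detecting an AE that occurs in 10% of patients. This reproduces: 1 − 0.9^24 = 92.0%. With the 8 patients who trigger the meeting, the same formula gives 1 − 0.9^8 = 57.0%, counting all 8 whatever cycle they have reached.

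**Infusions after the trigger.** Part 2 has 24 patients (Section 8.1) and up to three infusions each in Cycles 3 to 5, so 24 × 3 = 72. Patient 8 is on Day 1 at the trigger, and patients 9 to 24 start no earlier. Cycles 3 to 5 of patients 8 to 24 therefore all lie ahead: 17 × 3 = 51, and 51/72 = 71%. This holds at any accrual rate. It is a ceiling, because progression or toxicity may end treatment early (Section 4.3.2.1).

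**What the meeting could contain.** The Part 2 footnotes to the Schedule of Assessments (Appendix 3) put Day 1 of Cycles 3, 4 and 5 at Days 71, 106 and 141, which is 70, 105 and 140 days after the first dose. Part 2 accrual is not stated, so I assume even spacing, no dose delays and no dropout. The gap between patients is 30.44/rate days. Patient i has been on trial for (8 − i) × gap days when patient 8 is dosed, and has reached Cycle k if that is at least 35(k − 1).

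| Patients per month | Days from first dose of patient 1 to patient 8 | Reached Cycle 3 | Reached Cycle 4 | Reached Cycle 5 |
|---|---|---|---|---|
| 4 | 53 | 0 of 8 | 0 | 0 |
| 3 | 71 | 1 of 8 | 0 | 0 |
| 2 | 107 | 3 of 8 | 1 | 0 |
| 1 | 213 | 5 of 8 | 4 | 3 |
| 0.5 | 426 | 6 of 8 | 6 | 5 |

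The break-even is a gap of 70/7 = 10 days, or 30.44/10 = about 3 patients per month. Above that rate no patient has reached Cycle 3 at the trigger.

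Reaching a cycle is not the same as being observed through it. At 3 per month the one patient is about 71 days from first dose, one day past the Cycle 3 infusion. At 2 per month the three patients are at about 107, 91 and 76 days, so only the first has passed the 105 days that end Cycle 3.

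**Scale of the extrapolation.** At dose level D, the Part 1 maximum is the 5 mCi dosimetry dose plus two treatment doses, 5 + 2D. The Part 2 maximum is 5D. At 10 mCi this is 25 against 50 mCi (ratio 2.0); at 85 mCi it is 175 against 425 mCi (ratio 2.4). These are maxima at the same level. If the Part 2 dose is set below the highest level tested, Part 1 patients at higher levels narrow the difference.

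**The case against.** Four stronger readings are tempting, and the documents do not support them.

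- **That Cycles 3 to 5 get no planned independent review at all.** At about 3 patients per month or slower, the meeting could include some patients at Cycle 3 or beyond. The Synopsis recruitment window, Q4-2021 to Q3-2023, is at most 24 months for up to 25 + 24 = 49 patients, about 2 per month across the trial. Part 2 alone could be faster or slower, but at that rate 3 of 8 have reached Cycle 3. The DMC also has a planned, independent evaluation of whether five cycles are feasible.
- **That Sections 3.1.1.1 and 4.4 contradict each other.** Section 3.1.1.1 says "The DMC will receive all SAE on an ongoing basis", but it belongs to the Part 1 escalation rules, and Section 4.4 also promises SAE sharing throughout Part 1. Read in place, they agree.
- **That two thirds of Part 2 dosing (16 × 5 = 80 of 120 infusions) is unreviewed.** That count includes Cycles 1 and 2, which Part 1 does test.
- **That the DMC is cut off after its meeting.** Section 4.4.1 still requires an immediate cumulative DMC review if its triggers are met, and Section 7.4.5.6 provides for prompt DMC notification.

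Two further points have force. The protocol gives no data cut-off for the meeting, so patient 8's Cycle 1 toxicity might be included. The Charter may also schedule further reviews. Finally, the number of DMC meetings in a single-arm, open-label expansion is a design choice, and AE collection and final analysis do not depend on it.

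These points narrow the concern without removing it. The feasibility evaluation extrapolates from two cycles and observes none of Cycles 3 to 5. The first trigger in Section 4.4.1 is the sponsor's judgement, with no threshold. The second allows a DMC opinion, but Section 4.4 no longer promises the DMC the SAEs on which to form one. Immediate action under Section 7.4.5.6, including DMC notification, is the sponsor's decision. None of these is a planned review.

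**Conclusion.** The concern holds in a limited form. The protocol schedules one Part 2 DMC meeting, triggered by a first dose, and commits to SAE sharing (and, on a natural reading, to unplanned meetings on request) only until then. No planned review is therefore assured to include observed Cycle 3 to 5 data. Up to 51 of the 72 possible infusions in those cycles (71%) fall after the trigger whatever the accrual.

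What the meeting would see of the earliest patients ranges from none at Cycle 3 (4 per month) to five of eight (1 per month). That range rests on assumed even accrual without delays or dropout. The conclusion concerns what the protocol guarantees; the Charter may guarantee more. It is worth acting on because repeated-dose safety is the Part 2 primary objective and the remedy is cheap.

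**What to change.** In Section 4.4:

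1. Extend the sharing of all SAEs with the DMC, and the right of the DMC or the Sponsor Safety Committee to call an unplanned meeting, to the end of Part 2 dosing.
2. Key the Part 2 review to repeated-cycle exposure, for example when a set number of patients have completed Cycle 3, or keep the present meeting and add one such review. Adding keeps the early look at the first eight patients. The number should be low enough that a useful share of later-cycle dosing is still ahead.
3. State the data cut-off for each Part 2 meeting. If the Charter already provides for any of this, say so in the protocol.

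The cost is protocol and Charter wording, continued forwarding of SAE reports that are already produced, and at most one extra DMC meeting. No dose, eligibility rule, endpoint or sample size changes.
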